### ***Intervention***

**Relaxation intervention delivered by the digital human.** Participants will interact with the digital human for 25 minutes. During this time, the digital human will guide participants through progressive muscle relaxation and guided deep breathing.

**Relaxation intervention delivered by the audiotapes.** Participants will be asked to listen to the audio recording on the computer to guide them through a relaxation intervention (the same progressive muscle relaxation and guided breathing script as the digital human) for 25 minutes.

**Control.** The control condition will not be provided with a relaxation intervention, only magazines while participants are told to wait and see how their skin recovers. Magazines have been used as a control condition in previous studies as a neutral activity to prevent participants from becoming too bored (Robinson et al., 2017).

In all conditions, the lights in the room will be dimmed to make the room more relaxing.

### ***Baseline Measures***

These are measured to describe the sample and control for any differences between groups, because these variables have been previously shown to affect healing and immune parameters (Law et al., 2020a, 2020b; Robinson et al., 2015).

**Demographics.** Participants will be given a demographics questionnaire which includes questions regarding age, weight, height, ethnicity, and education level. Collecting data on these variables will allow for subgroup analysis and comparisons of the groups at baseline.

**Health behaviours.** Participants will be given a questionnaire that includes questions about alcohol consumption, physical exercise, diet, smoking status, and sleep. Alcohol consumption will be assessed from 1 (never) to 6 (every day) in the past three months. Participants will be asked how often they did physical exercise for more than 30 minutes in an average week from 1 (never) to 8 (every day). Diet will be assessed from 1 (very poor) to 5 (very good) in the past week. Participants will be asked to give their smoking status and the number of hours slept in the past 24 hours.

**Perceived stress.** The Perceived Stress Scale (PSS) measures the appraisal of how stressful situations in one's life are perceived (Cohen, 1983), and will be assessed at baseline only. It uses a 10-item Likert scale to rate how often respondents felt or thought a certain way in the last month from 0 (never) to 4 (very often). Scores are totalled across items and range between 0 and 40. High scores on the PSS indicate participants are experiencing a greater level of perceived stress. The scale has shown good reliability ( $\alpha > .70$ ) and validity in different ethnicities and clinical samples (Lee, 2012).

### *Primary outcome measures*

**Tape stripping and SBR.** The final SBR value for each site is determined by the TEWL readings from the three time-points. An overall TEWL reading comes from averaging 20 consecutive measurements with a standard deviation below 0.5 for each site and time point. To get the SBR percentage from the TEWL readings the following formula is used:  $(TEWL_{elevated} - TEWL_{recovery}) / (TEWL_{elevated} - TEWL_{baseline}) \times 100$  (Robles, 2007; Robles et al., 2009). A higher percentage means a higher SBR during the intervention period (faster wound healing). SBR values will be excluded if there is incomplete data, are more than two standard deviations above the mean, or sites are not within 30g/m^2h of each other (Law et al., 2020a). This outcome has concurrent validity with gravimetrically assessed absolute water loss rates (Fluhr et al., 2006).

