## **Hypotheses**

1. It is hypothesised that both the digital human and audiotape conditions will have improved SBR after a tape-stripping wound, as assessed by trans-epidermal water loss (TEWL), compared to the control group, who did not receive a relaxation intervention (only magazines).
2. It is hypothesised that there will be no differences in SBR after a tape-stripping wound, as assessed by TEWL, between the digital human and audiotapes condition.
3. It is hypothesised that the relationship between relaxation and SBR will be mediated by levels of stress (biological, physiological, and self-reported) .
4. It is hypothesised that the digital human condition will have greater improvements in anxiety, stress, pain and relaxation levels and better compared to the audiotape delivery and magazines (control group).

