### ***Participants***

**Inclusion criteria.** Participants will be eligible for inclusion if they are over the age of 18 and can speak, read, and write in fluent English.

**Exclusion criteria.** Participants will be excluded from the study if they are allergic to adhesive tape, have any inflammatory skin diseases/immunological-related health problems,

are taking medication that affects immune functioning (e.g., prednisone), are pregnant, over the age of 60 or have hearing difficulties or vision loss.

**Sample size.** The sample size was calculated using G\*Power (Faul et al., 2007) with a *mixed factorial ANOVA*. A power level of .80 and a two-tailed significance level of  $\alpha = .05$  was chosen, with an expected effect size of  $f = 0.30$ , based on previous research investigating a relaxation intervention on SBR (Robinson et al., 2017). Using these parameters gives a required sample size of 75. Like previous tape-stripping studies, this will be increased by 20% to account for possible errors in the TEWL measurements (Law et al., 2020), giving a final sample size of 90 participants (30 participants per group).

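### The primary outcome is trimmed only in its favourable tail, at two SDs above an undefined mean: a pooled mean shrinks the effect modestly, per-arm means inflate type I error

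*Protocol*

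**What the plan says.** The exclusion rule is in Protocol, Primary outcome measures: "SBR values will be excluded if there is incomplete data, are more than two standard deviations above the mean". A third criterion, on agreement between sites, follows in the same sentence. No lower limit is given for SBR, and the mean is not described as pooled, per arm or over sites.

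The same section fixes the direction of the outcome, "A higher percentage means a higher SBR during the intervention period (faster wound healing", and its unit, "The final SBR value for each site is determined by the TEWL readings from the three time-points". Under Procedure, each participant has three stripped sites.

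The Hypotheses section expects that "both the digital human and audiotape conditions will have improved SBR after a tape-stripping wound" relative to control, and that "there will be no differences in SBR after a tape-stripping wound, as assessed by TEWL, between the digital human and audiotapes condition".

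The sample size text under Participants adds a margin: "this will be increased by 20% to account for possible errors in the TEWL measurements". Nothing in the protocol provides for an analysis that keeps the excluded values.

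**The concern.** Whether a value enters the primary analysis depends on the value itself, which is measured after randomisation and after the intervention. The cut falls only on the side that counts as success. If relaxation works and the cut-off is common to all arms, more values lie above it in the relaxation arms than in control, so exclusion differs by arm and the difference is underestimated. If the cut-off is set within each arm, exclusion is balanced, but each arm's spread is cut artificially and the F test becomes too liberal. The two readings fail in opposite ways, and the text does not choose between them. The choice could therefore be made once the data are in hand, by a researcher who is no longer blinded after the envelope is opened.

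**Working it through.** **Inputs from the protocol.** Three arms, 30 per arm, f = 0.30, two-tailed alpha 0.05, power 0.80, 75 before and 90 after the 20% increase; upper cut at mean + 2 SD. **Assumptions.** Within-arm SD of 1; normal data, with lognormal data as a right-skewed check; one SBR value per participant analysed by one-way ANOVA, except in step 5.

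**1. The plan's own figure.** The protocol says "Using these parameters gives a required sample size of 75". For the between-groups test of a repeated-measures ANOVA, λ = f²·N·m / (1 + (m − 1)ρ). With m = 3 and an assumed ρ = 0.5, λ = 0.09 × 75 × 3 / 2 = 10.125, and power is 0.803. So 75 reproduces, and 75 × 1.2 = 90. On one value per participant, f = 0.30 at N = 90 gives power of about 0.71. That is the untrimmed benchmark below, not a restatement of the planned power.

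**2. Effect implied by f = 0.30.** The hypotheses give means (0, d, d). The SD of these is d√2/3, so d = 0.30 × 3/√2 = 0.636 SD.

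**3. Pooled cut, one value per participant, normal data.**
- Pooled mean = 2d/3 = 0.424; pooled SD = √(1 + 0.09) = 1.044; cut-off = 0.424 + 2 × 1.044 = 2.512.
- Removed in control: P(Z > 2.512) = 0.6%. Removed in each relaxation arm: P(Z > 2.512 − 0.636) = 3.0% (2.9% in simulation at 30 per arm). Per trial that is about 30 × 0.006 = 0.2 control values and 60 × 0.030 = 1.8 relaxation values.
- Mean after truncation = μ − φ(c − μ)/Φ(c − μ). Control: 0 − 0.017 = −0.017. Relaxation: 0.636 − 0.071 = 0.566.
- Difference = 0.566 + 0.017 = 0.583 SD, which is 8.4% below 0.636. Over f = 0.2 to 0.5 the loss runs from 9.6% to 6.1%.

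**4. Simulation, 30 per arm (20,000 runs with an effect, 8,000 under the null).**

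| Data | Rule | Difference (SD) | Power | Type I error |
|---|---|---|---|---|
| Normal | none | 0.635 | 0.703 | 0.049 |
| Normal | upper cut, pooled | 0.583 | 0.662 | 0.046 |
| Normal | symmetric ±2 SD, pooled | 0.511 | 0.582 | 0.047 |
| Normal | upper cut, per arm | 0.636 | 0.740 | 0.077 |
| Skewed | none | 0.637 | 0.727 | 0.043 |
| Skewed | upper cut, pooled | 0.580 | 0.869 | 0.047 |
| Skewed | upper cut, per arm | 0.636 | 0.896 | 0.125 |

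Under the null with a pooled cut and normal data, about 2.2% is removed from every arm. In the skewed pooled case with an effect, 2.8% of control and 5.3% of relaxation values go. A repeat of the per-arm case gave type I error of 0.073 (normal) and 0.128 (skewed).

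**5. Pooled cut applied per site.** Three sites per participant, remaining sites averaged, d = 0.636 SD of the participant mean, normal data, between-site correlation 0.3 to 0.9 (assumed, because the protocol gives none). The effect shrinks by 5-7%. Power falls by about 1-2 points (71% to 70% at correlation 0.5). At most 1.3% of relaxation participants lose all three sites (0.2% at correlation 0.5).

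**The case against.** The rule is pre-specified and attributed to an earlier tape-stripping trial. Under a pooled mean it is conservative: type I error stays nominal, so it cannot manufacture a superiority claim for the first hypothesis. The shift of 0.053 SD is small beside the standard error of the relaxation-minus-control contrast, √(1/60 + 1/30) = 0.22 SD. Very high values may also be artefacts. SBR divides by elevated minus baseline TEWL, and stripping may stop at 40 tapes before the target rise is reached, so small denominators are possible. If 5% of values in every arm carried a gross upward error of 4 SD (an assumption), the rule would raise power from 48% to 61%, although the estimate would still shrink by about 7%.

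Most of this stands, and it limits the size of the point. It does not rescue the rule. Precedent is not evidence of validity. A small denominator can equally produce very low or negative values, which the rule keeps. The section already has measurement-based criteria, and the 20% increase covers lost numbers, not selective loss. The conservative argument also fails if the mean is per arm.

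A reader might infer more than the protocol supports:
- **That the best healers are thrown out of the trial.** SBR is defined per site, so the natural reading drops a site value and keeps the participant; and some high values may be artefacts rather than strong healing.
- **That the effect shrinks by a quarter.** Losses of about 25% arise only if a proportional effect on skewed data, or a 30% subgroup of strong responders, is assumed. The protocol supports neither.
- **That bias towards zero is certain.** It needs both a real effect and a pooled mean.

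**Conclusion.** The point holds with modest size; it should be fixed, but it does not invalidate the trial. With a pooled mean and the hypothesised effect, the difference is underestimated by about 6-10% per participant or 5-7% per site, at a cost of about 1-5 power points under normal data. With right-skewed data the estimate still shrinks by about 9%, while power can rise (0.73 to 0.87) because variance falls. With per-arm means the estimate is not attenuated, but the nominal 0.05 test runs at about 0.07-0.08 (normal) or 0.13 (skewed).

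These sizes rest on f = 0.30 with two equal relaxation arms, on the assumed data shapes and between-site correlations, and on a one-way comparison of SBR. That the rule is one-sided, depends on the outcome and leaves its mean undefined rests on the text alone.

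**What to change.** - Remove the two-SD rule from the primary analysis and keep all valid site SBR values.
- Exclude readings only on measurement quality: the existing SD criterion for the 20 consecutive readings, incomplete data, and documented faults, judged blind to arm and SBR.
- Do not substitute a symmetric two-SD cut. In the normal case it attenuates the effect by about 20%, against about 8% for the present rule.
- Report two sensitivity analyses: the two-SD rule with its reference stated (pooled mean, site level), for comparability with earlier work, and a robust or rank-based analysis. Show exclusions by arm.
- Settle this before any outcome data are examined.

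The cost is wording plus two extra analyses. The downside is that some artefactual high values, for example from a small elevated-minus-baseline denominator, stay in the primary analysis. They can widen the interval and, if SBR is strongly skewed, lower power. The robust sensitivity analysis addresses that.

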### *Secondary outcome measures*

**Biological Measures.** Salivary cortisol and alpha-amylase are reliable and valid measures of stress-related biological markers of stress if standardised procedures (as above) to reduce confounders are used (Strahler et al., 2017). The collection of these samples is necessary to investigate whether the intervention had any effect on physiological stress and test the secondary hypothesis regarding stress mediating the relationship between relaxation and wound healing. Having these measures is important for further understanding of the underlying mechanisms through which relaxation works on stress and wound healing.

Saliva samples will be obtained at three-time points; baseline, after tape-stripping and after the intervention period, using standardised SaliCaps collection devices (IBL, Hamburg, Germany). Participants will be asked to rinse their mouth with water beforehand and not

swallow for two minutes to collect saliva in their mouth naturally, using the passive drool technique, before transferring their saliva into the SaliCap. After collection, the saliva samples will be stored at  $-20^{\circ}\text{C}$  at the University of Auckland and then shipped for analysis on dry ice to the University of Vienna. Cortisol concentrations will be determined using commercial enzyme-linked immunosorbent assay (ELISA, IBL, Hamburg, Germany), while alpha-amylase will be determined by a kinetic colorimetric test with reagents from Roche (Roche Diagnostics, Mannheim, Germany; Law et al., 2020a; Robinson et al., 2017).

**Physiological measures.** Participants will wear a wrist sensor (Empatica E4) which will continuously measure blood volume pulse and electrodermal activity for the duration of the session. Blood volume pulse will be converted into a measure of heart rate. Electrodermal activity will be used to measure changes in electrical resistance in the skin (skin conductance). Heart rate and skin conductance will be used as physiological measures of stress and relaxation.

**Psychological measures.** Participants will be given a visual analogue scale at the three time points to measure participants level of relaxation, stress, anxiety, and pain where they are required to mark a cross on a 100mm line how they are currently feeling. Scores are derived by using a ruler and measuring the distance (in mm) from the "not at all" anchor to the cross the participant placed on the line. A high score indicates that at the current time the participant has greater intensities of felt stress, anxiety, and pain and lower levels of relaxation.

The relaxation scale ranges from "not relaxed at all" to "extremely relaxed", the stress scale from "not at all stressed" to "extremely stressed", the anxiety scale from "not at all anxious" to very anxious" and the pain scale from "no sensation of pain" to "most sensation

of pain imaginable". These measures have been used in previous tape stripping and psychological intervention studies to assess participant psychological state (Law et al., 2020a; 2020b; Robinson et al., 2015).

**Relaxation Delivery Feedback.** There will be two visual analogue scales (on a 100mm line) asking about participant's satisfaction and engagement during the relaxation session from "not engaging at all" to extremely engaging" and "not at all satisfied" to very satisfied". The second part of this section is qualitative and will ask participants to write what they liked about the session's delivery and how it can be improved. These questions have been adapted from Loveys and colleague's feasibility study investigating digital humans and CBSM (in prep). Including this questionnaire is necessary to understand how people respond to the digital human.

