### *Analysis*

A mixed factorial ANOVA will be conducted to assess differences in SBR between conditions, in addition to an ANCOVA (to control for covariates related to SBR rates such as age, number of strips of tape, and levels of skin barrier impairment; Law et al., 2020; Robinson et al., 2017). For the secondary outcomes (biological, physiological, and psychological measures), mixed factorial ANOVAs will be conducted to analyse the main and interaction effects of time-point and condition. The data will be checked for violations of the normality assumption before analysis. To investigate whether psychological and physiological stress levels mediate the relationship between the delivery condition and SBR, separate exploratory mediational analyses will be conducted.

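### The protocol contradicts itself on the direction of the relaxation visual analogue scale: its scoring rule and anchors make a high score mean more relaxed, its interpretation sentence says less relaxed

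*Protocol*

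**What the plan says.** All of the conflicting text is in the Protocol, under Secondary outcome measures, in the description of the psychological measures. Relaxation, stress, anxiety and pain are each marked on a 100 mm line at three time points.

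- Scoring: a ruler is used, "measuring the distance (in mm) from the 'not at all' anchor to the cross the participant placed on the line".
- Relaxation anchors: "The relaxation scale ranges from 'not relaxed at all' to 'extremely relaxed".
- Stress anchors, for comparison: "the stress scale from 'not at all stressed' to 'extremely stressed". The anxiety and pain lines likewise run from none to a maximum.
- Meaning of a high score, given once for all four lines: "greater intensities of felt stress, anxiety, and pain and lower levels of relaxation".

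The relaxation item is put to use elsewhere. The tertiary aim lists relaxation among the outcomes to be compared between delivery methods. Hypothesis 4 is directional and predicts that the digital human condition will show "greater improvements in anxiety, stress, pain and relaxation levels" relative to the audiotape and the magazine control. Under Analysis, the secondary outcomes, including the psychological measures, are handled as follows: "mixed factorial ANOVAs will be conducted to analyse the main and interaction effects of time-point and condition". Neither section mentions reversing the relaxation score.

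**The concern.** One sentence gives the meaning of a high score for four lines, but one of the four runs the other way. Stress, anxiety and pain start at none and end at a maximum of something undesirable, so a high distance is bad. Relaxation starts at none and ends at a maximum of something desirable, so a high distance is good. The sentence treats relaxation as if it had been reverse-scored, and the protocol does not say that it is.

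At stake is the direction of a named outcome in a directional hypothesis. Whether a condition improved relaxation cannot be judged until it is settled which end of the score is improvement. The error would also be silent: as shown in the check, a reversed scale gives identical test statistics, so nothing in the ANOVA output would alert the analyst.

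**Working it through.** The protocol gives no figure to reproduce here. The check applies its scoring rule to its anchors and compares the result with its interpretation sentence.

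**Inputs**, all from the psychological measures paragraph: line length 100 mm; score x = distance in mm from the lower anchor; the anchors of each line; the stated meaning of a high score.

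**Step 1. Direction of each item.**

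| Item | x = 0 | x = 100 | High x by rule and anchors | High score by the sentence | Agree? |
|---|---|---|---|---|---|
| Stress | none | extreme | more stress | more stress | yes |
| Anxiety | none | very high | more anxiety | more anxiety | yes |
| Pain | none | worst imaginable | more pain | more pain | yes |
| Relaxation | none | extreme | more relaxation | less relaxation | **no** |

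The lower relaxation anchor is not worded identically to the generic one in the scoring rule, but it is the only end of that line to which the rule can refer. The wording therefore leaves no room for the opposite reading.

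**Step 2. One mark (assumed value).** A cross 80 mm from the lower relaxation anchor scores x = 80. By the anchors this person is close to the most relaxed end. By the sentence, a score of 80 is high and so means little relaxation. The sentence would be correct only for the reversed score, R = 100 − x = 100 − 80 = 20, where a low R goes with high relaxation.

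**Step 3. A change over time (assumed values).** Suppose a group mean moves from x = 60 to x = 80.

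- By rule and anchors: 80 − 60 = +20 mm, a gain in relaxation.
- On the reversed score: (100 − 80) − (100 − 60) = 20 − 40 = −20 mm, which the sentence correctly reads as a gain.
- Unreversed score read by the sentence: +20 mm, reported as a 20 mm loss of relaxation.

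The 20 mm is only an illustration; the protocol gives no expected change. The same flip applies to any size of change.

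**Step 4. Effect on the planned test.** With R = 100 − x, any contrast of means whose weights sum to zero changes sign only: for two conditions, R̄₁ − R̄₂ = (100 − x̄₁) − (100 − x̄₂) = −(x̄₁ − x̄₂). Sums of squares are built from squared deviations, and (−1)² = 1, so every sum of squares for time-point, condition and their interaction is unchanged. Hence F and p are unchanged. Only the sign of the means, changes and contrasts, and therefore the wording of the conclusion, depends on the direction chosen.

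**The case against.** The strongest reply is that this is a drafting slip in a descriptive clause. The clause is right for three of the four lines, and the scoring rule and the anchors stand in the same paragraph. Together they fix the direction of the raw score, so an analyst with the printed form in hand would probably see which way the line runs. It can be added that a reverse-coding step belongs in a statistical analysis plan or data dictionary, and the analysis plan is not available here.

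Much of this stands. The reversal is conditional: it happens only if the unreversed score is read by the interpretation sentence. A slip is the likeliest explanation, although an intended but unstated reversal cannot be excluded. The absence of a reverse-coding step would not be a fault by itself. What the reply does not remove is the contradiction. The protocol chose to fix the scoring rule, the anchors and the meaning of a high score, and these conflict for one item. A later document could explain the conflict, but the protocol's own text would remain wrong.

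A reader might infer more than the document supports:

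- *That the relaxation result is reversed outright.* It is not; that depends on how the score is read.
- *That effects would cancel in a combined score.* No composite of the four lines is planned; each is described separately.
- *That a manipulation check is compromised.* The protocol does not give the relaxation item that role.
- *That the mediation analysis is compromised.* The mediator named in the secondary aim, hypothesis 3 and the Analysis section is stress. The relaxation item is not named as a mediator, and these analyses are called exploratory.
- *That an ANCOVA is affected.* The ANCOVA is specified for skin barrier recovery; relaxation goes to a mixed factorial ANOVA.

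**Conclusion.** The contradiction is real and lies within one paragraph. As written, the interpretation rule is wrong for the relaxation item under the stated scoring and anchors. Followed literally on unreversed scores, it reverses the direction of the relaxation result under the tertiary aim and hypothesis 4, with the magnitude kept and the sign flipped.

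The scope is narrow: one of the four visual analogue items in hypothesis 4. The ANOVA F and p values, the other three items, the sample size, and hypotheses 1 and 2 on the primary outcome do not depend on it. The conclusion assumes that the scoring rule applies to all four lines, as the text states, and that no reversal is applied before analysis, since none is stated. If a reversal is in fact intended, the sentence is right and the scoring description is incomplete; the text needs correcting either way.

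**What to change.** Choose one of two definitions and write it into the paragraph:

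1. Keep the measured distance as the analysed score. State that a high score means greater stress, anxiety and pain and, for the relaxation item, greater relaxation (0 = not relaxed at all, 100 = extremely relaxed). Relaxation then runs in the opposite direction to the other three items in terms of benefit, and the text should say so.
2. Define the analysed relaxation score as 100 minus the measured distance. The present sentence on high scores then becomes correct for all four items.

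Use the chosen definition in the mixed factorial ANOVA of the psychological measures, and in any exploratory mediation analysis that happens to use the item. Put it in the data dictionary and label tables and figures with the direction of benefit.

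The cost is one sentence in the protocol and a matching line in the data dictionary and analysis code. The printed scales, data collection and sample size do not change. It is best settled before data entry.
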